Protocol Title: From intention to behavior with i2be:

a randomized controlled trial protocol for an app-based physical activity intervention

Short Title: i2be

Version: 2

Date: 29-03-2021

Project leader: [name] ([contact])

Sponsor: This study was commissioned by the Erasmus Medical Center and the Erasmus University Rotterdam through the Smarter Choices for Better Health Initiative (Action Line Prevention).

Subsidizing party: Funding for the study was by the Smarter Choices for Better Health Initiative (Action Line Prevention) and the Erasmus Trustfonds.

Summary

Rationale: Physical activity is an important determinant of cardiovascular health. Therefore, health behavior interventions targeting physical activity are highly warranted. Most interventions have limited and short-term effects, likely because they fail to bridge the intention-behavior gap.

Objective: The current study will test a dual system theory- and evidence-based e-health intervention, and additionally, provide important insight into the contribution of volitional and automatic processes in bridging the intention-behavior gap and achieving sufficient and sustained physical activity.

Study design: The effectiveness of the intervention will be tested using a three-arm randomized controlled trial implemented through an app.

Study population: Women with a prior hypertensive disorder of pregnancy

Intervention: Following i2be app registration and stratification on baseline factors, participants will be randomly allocated (1:1:1) in-app to the control group, treatment 1, or treatment 2. The control group receives the module 'Get Informed' consisting of usual care, i.e. knowledge provision. In addition to the module 'Get Informed', treatment 1 receives the module 'Get Motivated' (targeting motivational processes), consisting of the behavior change technique (BCT) motivational interviewing-based counselling. In addition to the modules 'Get Informed' and 'Get Motivated', treatment 2 receives the module 'Get Activated' (targeting volitional processes), consisting of the BCTs action planning training and reminders, coping planning training, and commitment training, and the module 'Get Energized' (targeting automatic processes), consisting of the BCTs mindfulness-based stress reduction and positive psychology.

Main study parameters/endpoints: The primary outcome is objectively measured weekly minutes of moderate-to-vigorous physical activity. Secondary outcomes include

objectively measured (resting heart rate) and self-reported physiology measurements (body mass index, waist-hip-ratio, cardiorespiratory fitness), as well as subjective well-being. Tertiary outcomes include self-reported mechanism of action variables in order to assess the mechanisms underlying the effects of BCTs. Objectively measured outcomes will be captured by Fitbit activity trackers (Fitbit Inspire 2), and all other outcomes measures will be self-reported into the i2be app. Outcome measures will be assessed at baseline, immediately post-intervention, at 3 months follow-up, and at 12 months follow-up. Physical activity will additionally be assessed at the intervention midpoint. Effectiveness will be determined by a modified intention-to-treat analysis. Additionally, a process evaluation will be performed immediately post-intervention.

Nature and extent of the burden and risks associated with participation, benefit and group relatedness: Not applicable.

1. Introduction and rationale

The reduction of cardiovascular disease (CVD) is a public health priority, as CVDs are among the leading causes of poor health worldwide [1]. Insufficient physical activity, poor dietary habits, tobacco, and alcohol use are some of the most important behavioral risk factors for CVD [1]. Cardio metabolic risk factors for CVD such as hypertension, overweight and obesity often go hand in hand with behavioral risk factors for CVD [2, 3]. Some cardio metabolic risk factors for CVD are specific to women, including hypertensive pregnancy disorders [4, 5]. For example, preeclampsia is a hypertensive pregnancy disorder complicating two to eight percent of pregnancies worldwide, leading to acute clinical consequences of maternal and neonatal morbidity and mortality, and a two to seven fold risk for CVD later in life in comparison to women with a normotensive pregnancy [6, 7].

A substantial proportion of CVD morbidity and mortality can be prevented by individuals leading healthy lifestyles [5, 8]. International guidelines advise adults to accumulate at least 150 minutes of moderate physical activity, 75 minutes of vigorous physical activity, or an equivalent combination of moderate- and vigorous-intensity physical activity (MVPA) per week [9]. Most people, and especially women, fail to meet these guidelines [1]. Therefore, the implementation of health behavior change interventions targeting MVPA are highly warranted [3]. Such interventions are likely to provide an especially high social return in women with hypertensive disorders of pregnancy, primarily due to the importance of optimizing the cardiovascular health of this population [5, 10-12].

Health behavior change interventions targeting MVPA are widely applied in the general population, rarely achieving large and long-term effects [13]. A potential explanation for the limited effects of these interventions are their lack of theoretical basis, and no systematic linking of evidence-based behavior change techniques (BCTs) to specific mechanism of action (MOA) variables [14]. Another explanation is their use of traditional socio-cognitive theories (e.g., self-determination theory, theory of planned behavior), which describe behavior as solely the result of deliberative (also called rational or conscious) psychological processes, with underlying MOA variables such as knowledge,

attitudes, or intention [15]. Indeed, while well-established deliberative theories reliably succeed at predicting behavioral intention, they regularly fail to predict actual behavior, leading to the infamous 'intention-behavior gap' [16]. A potential explanation for this shortcoming is their underestimation of automatic (also called impulsive or non-conscious) processes involved in health behavior, with underlying MOA variables such as affect, stress, and habit [15, 17].

The notion that behavior, at least in part, is influenced by factors beyond individual awareness is not new – the school of thought of behaviorism is a prominent example [18]. However, interest in the integration of both types of processes into one theory is relatively new, partly brought about by deliberative theories' inability to provide a full account of human behavior, and partly by developments in the understanding of automatic processes [15]. Dual-system theories account for both types of processes, i.e. automatic processes generating impulses, and deliberative processes controlling these impulses [15, 19-21]. The present intervention is based on a specific dual-system theory, i.e. the integrated behavior change (IBC) model [22].

The IBC model integrates insights of well-established health behavior theories to explain the workings of deliberative processes and automatic processes involved in physical activity [22-24]. The IBC model separates deliberative processes into two sub-types, i.e. motivational and volitional processes, thereby differentiating between three main types of processes in total [22]. This clear distinction between pre-intentional (motivational) and post-intentional (volitional) processes, as well as accounting for automatic processes, may be key in bridging the 'intention-behavior gap' [16]. Since the development of the first IBC model, several observational studies have updated the core model and used it to explain a plethora of health behaviors, from fat and sugar intake to sunscreen use [25-33].

The current intervention is among the very first interventions to use the IBC model as its theoretical framework [34]. Furthermore, we have systematically selected BCTs linking to the MOA variables described by the IBC model [14, 35]. The selection of BCTs was

guided by systematic literature reviews, meta-analyses and evidence syntheses examining the association between BCTs and theory [36] and theoretical domains [37], intervention effect evaluations [38, 39], intervention process evaluations [40], and previous research showing the effectiveness of these BCTs [41-49].

When it comes to the delivery of interventions, e-health interventions have several advantages over face-to-face interventions, i.e. they are comparatively low cost, have a wide reach, and provide flexibility in intervention location and time [50, 51]. Previous e-health interventions that used a tailored design, i.e. provided participants with primary task support, dialogue support and social support, showed superior effects in fostering user engagement [52, 53] and in increasing MVPA [51, 54] over interventions that took a non-tailored approach. Due to the considerations above we chose to deliver the current intervention in e-health format, more specifically, as a tailored mobile phone application (app) providing primary task support and dialogue support that can be downloaded to any smartphone.

The aim of the study is to determine the effectiveness of a dual system theory- and evidence-based e-health intervention using a three-arm randomized controlled trial (RCT). Furthermore, our study design will allow us to gain important scientific knowledge regarding the theoretical framework on which the intervention was based (i.e. the IBC model) by providing insight into the contribution of motivational, volitional, and automatic processes in leaping across the intention-behavior gap and achieving sufficient and sustained physical activity.

2. Objective

Primary objective: The objective of the study is to determine the effectiveness of a dual system theory- and evidence-based e-health intervention to sustainably increase physical activity using a three-arm randomized controlled trial (RCT).

Secondary objective: Our study design will allow us to gain important scientific knowledge regarding the theoretical framework on which the intervention was based (i.e. the IBC

model) by providing insight into the contribution of motivational, volitional, and automatic processes in leaping across the intention-behavior gap and achieving sufficient and sustained physical activity.

3. Study design

The randomized controlled trial (RCT) will have a duration of eight weeks. All participant interactions (e.g. sign up, intervention, data collection, and participation incentives) occur via the purpose-built i2be app. The user-interface of i2be shows a diverse range of women of ethnic backgrounds and ages (20-50 years) representative of the population, and uses female voice-overs in the instruction video and audio clips. The modules 'Get Informed', 'Get Motivated', 'Get Activated' and 'Get Energized' consist of interactive, fully automated activities each week, i.e. participants are prompted to reflect and engage with the activities, without interaction with the researcher.

4. Study population

4.1. Population base

The population base will consist of women who have experienced a hypertensive disorder of pregnancy [4-6]. Given that the associated CVD risk is largest for women with a history of preeclampsia, especially severe preeclampsia [4, 6], we first draw participants from this population. If necessary, we will further include women with other hypertensive disorders of pregnancy in a stepwise manner (see Recruitment).

4.2. Inclusion criteria

In order to be eligible for participation in the trial, a participant must meet the following criteria:

 Experienced a hypertensive disorder of pregnancy (e.g. preeclampsia, eclampsia, HELLP syndrome) in the past.

4.3. Exclusion criteria

A person who meets any of the following criteria will not be eligible for participation in this study:

C1. Research Protocol i2be Version 2 dd 29-03-2021

- <18 years of age
- Pregnant at time of inclusion
- <3 months post-partum
- Any physical health limitations preventing physical activity (e.g. illness, injury, surgery, rehabilitation)
- No working knowledge of Dutch or English language
- No possession of a smartphone

4.4. Sample size calculation

A meta-analyses of recent smartphone-based physical activity interventions found a small to medium average effect size (standardized mean difference) of 0.31 on daily minutes of physical activity [55]. The effect sizes in individual studies ranged between -0.29 to 0.70. We expect the main treatment effect in our study (T2 v C) to be towards the higher end of this range. Our second treatment effect (T2 versus T1) is expected to be somewhat smaller. Given this, we aim to recruit 600 participants to the trial, randomized in a 1:1:1 allocation ratio to the three arms (200:200:200 participants). The average attrition rate in previous web-based physical activity interventions was 20% [56]. However, as we incentivize participation throughout the duration of our study using both psychological and tangible rewards, we estimate that attrition will be 15% in our study. This would leave us with a final total sample size of 510, once attrition is accounted for. Taking into account the potential maximum deviation from a 1:1:1 allocation ratio which may arise due to the stratified block randomization procedure, our intended sample size (n=600) will give us power to detect effect sizes greater than or equal to the average effect found in the metaanalysis (0.31), which should be adequate to detect our main treatment effect of T2 versus C.

4.5. Recruitment

In the Netherlands, unique cardiovascular follow-up and care is provided to women with prior severe preeclampsia at the multidisciplinary Follow-Up Pre-Eclampsia Outpatient Clinic (FUPEC) of the Erasmus MC, the only clinic of its kind in the country [57]. There are currently around 1000 women involved in the clinic with an additional 100 to 150

women enrolling each year. An email to participate in the RCT will be sent to all FUPEC participants by their health care professionals, containing a short description of the study, an introduction video to the i2be app, and a link to an eligibility questionnaire (for more detail, see section on Implementation). In case the intended sample size (n=600) cannot be fully recruited from the FUPEC clinic, further recruitment will take place through the national patient organization for women with a history of preeclampsia (Hellp Stichting). Subsequent venues for recruitment include recruitment through the Department of Gynecology and Obstetrics (Erasmus MC), first among women with prior (non-severe) preeclampsia, and second among women with other hypertensive disorders of pregnancy [4], as well as similar departments of regional hospitals.

Invited women are informed that participation in the trial is voluntary, and that declining to participate does not affect their care from the Erasmus MC (or other hospitals). Women who choose to participate will be asked to sign an informed consent for trial participation and use of data for research purposes. Participants are informed that they may leave the trial at any point in time without having to provide a reason and without consequences for their care.

5. Treatment of subjects

All participants receive the components specified under standard treatment. Only participants in treatment 1 and treatment 2 receive the relevant investigational treatments. Participants are not prescribed, but are solely advised physical activity and all other activities, and participants are free to deviate from this advice.

5.1. Standard treatment

5.1.1. Get Informed

All participants use the i2be app and their Fitbit MVPA tracker. Participants will need to sync their Fitbit with the i2be app on a weekly basis for optimal data collection. All participants receive the module 'Get Informed' consisting of usual care. More specifically, information is provided on a) the international guidelines, examples, and health effects of physical activity, b) the relationship between hypertensive disorders of pregnancy,

increased risk of cardiovascular events, and physical activity, and c) support available for women with a prior hypertensive disorder of pregnancy.

5.1.2. Incentives

For all participants, the completion of modules and outcome measures and syncing of the Fitbit (i.e. trial participation) are incentivized with a virtual point system (i2be points) resulting in psychological rewards, i.e. progress though virtual levels of achievement and the receipt of digital trophies through the app. The virtual i2be points are further used to qualify for tangible rewards. For every week of the intervention and follow up measurement points, participants qualify to enter into a weekly raffle for a self-selected physical activity-related voucher (i.e. Decathlon.nl, Sportenfitcadeu.nl, Fysiosupplies.nl), under the condition that they earn the maximum i2be points for that week. The value of these vouchers increases from 25€ during the intervention to 30€ for the two final follow-up measurement points (i.e. 3- and 12-months post intervention) to encourage participants to engage in long-term follow up. Lastly, conditional on reaching a threshold of accumulated i2be point, participants qualify to keep the Fitbit at the end of the trial.

5.1.3. Objective measures

The primary outcome of this research project is objectively measured MVPA, as measured by the Fitbit. One of the secondary outcomes is objectively measured resting heart rate, also measured by the Fitbit.

5.1.4. Home measurements manually entered into app

See appendix F1 for home measurements manually entered into app.

5.1.5. Questionnaires filled in within app

See appendix F1 for questionnaires.

5.2. Investigational treatment

5.2.1. Treatment 1

In addition to receiving standard treatment, treatment 1 receives the module 'Get Motivated' (targeting motivational processes), consisting of the behavior change technique (BCT) motivational interviewing-based counselling. Participants receive an interactive, fully automated activity each week, consisting of content-based motivational interviewing techniques, namely: Running Head Start, Importance Ruler, Confidence Ruler, Looking Forward, Hypothetical Thinking, Query Extremes, Identifying Past Successes, Identifying Strengths, Values Exploration, Normalizing, and Goal Attainment Scaling [58].

5.2.2. Treatment 2

In addition to receiving standard treatment and the module 'Get Motivated', treatment 2 receives the module 'Get Activated' (targeting volitional processes), consisting of the BCTs action planning training and reminders, coping planning training, and commitment training. Participants receive interactive, fully automated activities each week: drop-down menus aid them in making action plans and coping plans [45]; they are reminded of their action plans by a reminder; they are asked to make a weekly MVPA goal, and offered the option to commit to that goal with their i2be points; and they are taught how to make their own commitments outside of i2be [59].

Furthermore, treatment 2 receives the module 'Get Energized' (targeting automatic processes), consisting of the BCTs mindfulness-based stress reduction and positive psychology. Participants receive four-minute audio clips of mindfulness-based stress reduction, namely Introduction to Mindfulness, Loving Kindness, Breath Awareness, Body Scan, Validation, Sensations, Gratitude, and Humor Therapy [49, 60]; and interactive, fully automated positive psychology exercises, namely Three Good Things, Kindness, Three Beautiful Things, Gratitude, Three Amusing Things, Savoring, Validation, and Power Posing [46, 47].

6. General considerations

6.1. Handling of dropouts

Participants can leave the trial at any time following consent without any consequences. Participants dropping out of the study will not be substituted. Following drop-out no further data will be collected.

7. Outcomes

7.1. Primary outcome

Outcome measures are collected at baseline, immediately post-intervention, 3 months follow-up, and 12 months follow-up (see appendix F1 for schematic overview of data collection during the trial). Physical activity will additionally be assessed at the intervention midpoint. The primary outcome of this research project is objectively measured MVPA, as measured by the Fitbit.

7.2. Secondary outcomes

Secondary outcomes consist of physiological and well-being measures. Resting heart rate will be measured by the Fitbit. Other physiological measures are taken at home and self-reported in i2be by participants, including body mass index, waist-to-hip ratio, and cardiorespiratory fitness. Text instructions on the correct performance of home measurements will be provided to participants in-app. A soft measuring tape will be sent to participants along with the Fitbit. Subjective well-being is self-reported in-app.

7.3. Tertiary outcomes

Tertiary outcomes include self-reported MOA variables in order to assess the mechanisms underlying the effects of BCTs.

7.4. Confounders

To adjust data-analyses for potential confounders, information on type of blood pressure condition, age, lactation status, household composition, education, trait self-control, and habit is self-reported in-app at baseline.

8. Interim analysis and stopping rules

We anticipate no safety issues with this study. As such, no interim analysis is planned, and no stopping rules are defined.

C1. Research Protocol i2be Version 2 dd 29-03-2021

9. Randomization

9.1. Stratification and randomization

Stratification and randomization will be carried out automatically by the app.

9.2. Allocation concealment mechanism

Inherent to the intervention and study design, participants will not be blinded to allocation. The research team will be blinded to the allocation of participants at the randomization stage and throughout the study.

9.3. Implementation

Following email invitation from health care professionals (in case of hospital recruitment) or the research team (in case of recruitment through patient organizations), interested participants click on a link in the email that will lead them to an eligibility questionnaire hosted on the researcher platform of Avegen (digital health company responsible for developing and hosting the researcher platform and participant app). Once eligibility has been established, the participant will be asked for informed consent. Following informed consent, participants will be asked their name, email address, and postal address to send the Fitbit and a soft measuring tape. Next, participants will receive an email from Avegen to download the i2be and Fitbit apps from the Google Play Store (for Android phones) or App Store (for iPhones), a pdf of the Welcome Pack, and a message that the Fitbit will be sent in the post mail. The Welcome Pack consists of instructions on the configuration of the Fitbit app and the i2be app, an explanation of the Fitbit device, and an explanation on the i2be points and reward system.

When using the i2be app for the first time, participants will be asked to choose their preferred language (Dutch or English) and register with their email address. Subsequently, participants will be stratified on two factors (i.e. on time since pregnancy [< 12 months post-partum versus ≥ 12 months post-partum] and self-reported baseline MVPA [low, medium, high]), and randomly allocated (1:1:1) in-app to one of the three intervention arms, i.e. the control group (C), treatment 1 (T1), or treatment 2 (T2). The

participants will be shown a 2 minute video that introduces i2be. The 8 week intervention period will then start.

10. Statistical analysis

10.1. Primary analysis

The primary analysis will be a modified intention-to-treat analysis, the deviation from a full intention-to-treat analysis being that we exclude participants with missing dependent variable data (available case analysis). Linear regression will be used to assess differences between groups. The main test of i2be is the test T2 versus C in order to gain insight into the effectiveness of targeting the three types of processes hypothesized to impact MVPA. Second, we aim to test differences between T2 and T1 to gain insight into the contribution of volitional and automatic processes over motivational processes only in bridging the intention behavior gap. Third, we will test the difference between T1 and C to gain insight into the differential effectiveness of targeting motivational processes compared to treatment as usual. Variation in MOA variables will be investigated to gain insight into the mechanisms underlying the effects of BCTs. Sensitivity analyses will be carried out to assess the robustness of results to the missing data strategy adopted.

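### The available-case primary analysis leaves out Fitbit MVPA already recorded for women who later have no outcome; a model using all observed MVPA rests on a weaker assumption

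*Protocol*

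**What the plan says.** Section 10.1 calls the primary analysis a modified intention-to-treat analysis and defines the modification: "we exclude participants with missing dependent variable data (available case analysis". The model is named in one sentence: "Linear regression will be used to assess differences between groups". The same section promises that "Sensitivity analyses will be carried out to assess the robustness of results to the missing data strategy adopted", without naming a method.

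On follow-up, section 6.1 says "Participants dropping out of the study will not be substituted" and "Following drop-out no further data will be collected".

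On the data available before a woman is lost, section 7.1 says "Outcome measures are collected at baseline, immediately post-intervention, 3 months follow-up, and 12 months follow-up", and adds "Physical activity will additionally be assessed at the intervention midpoint". Section 5.1.1 applies to all arms: "Participants will need to sync their Fitbit with the i2be app on a weekly basis for optimal data collection".

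Section 7.4 lists the covariates collected for adjustment. Fitbit MVPA at baseline is not among them. Section 9.3 stratifies on self-reported baseline MVPA and time since pregnancy. Section 4.4 plans for 15% attrition and mentions 20% in earlier web-based interventions.

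**The concern.** A woman who leaves in week 6 can have a baseline value, a midpoint value and several weeks of the outcome variable on record. Under section 10.1 she contributes nothing to the end-of-intervention comparison. The comparison is then between those still measured in each arm, not between the groups as randomised.

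This does harm only under a condition: missingness must depend on MVPA differently by arm, in a way the model covariates do not absorb. The protocol gives some reason to take that seriously. Participants know their allocation (section 9.2). The workload is one module in the control arm, two in treatment 1 and four in treatment 2 (sections 5.1 and 5.2). If less active women in treatment 2 are more likely to be lost than less active controls, the T2 versus C estimate is too favourable. The reverse pattern would bias it the other way.

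**Working it through.** **Step 1. The plan's own figure.** 600 × (1 − 0.15) = 510, as section 4.4 states, or 170 per arm if loss is equal. Assuming two-sided alpha 0.05 (the protocol states none), 170 per arm gives 81.5% power for a standardised difference of 0.31. The sample size already covers the loss of numbers. What remains is bias.

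**Step 2. Inputs for the bias check.** From the protocol: 200 per arm, a planned effect of 0.31 SD, and MVPA at baseline, midpoint and post-intervention. Assumed, because the protocol does not give them: SD 1, a common correlation of 0.6 between the three measurements, no true effect, and drop-out after the midpoint by a logistic model. The slopes in the tables are the increase in log-odds of drop-out per SD lower MVPA.

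**Step 3. Estimators.**
- Unadjusted: mean of T2 minus mean of C among women with an observed outcome.
- Baseline-adjusted: regression of the outcome on arm and baseline MVPA among the same women.
- All observed MVPA: within each arm, regress the outcome on baseline and midpoint MVPA among women with an outcome, predict for everyone randomised, then take the difference in means.

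**Step 4. Drop-out driven by midpoint MVPA, bias in SD.**

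| Loss C / T2 | Slope C / T2 | Unadjusted | Baseline-adjusted | Baseline and midpoint |
|---|---|---|---|---|
| 15% / 15% | 0.5 / 1.0 | +0.038 | +0.015 | within 0.004 |
| 15% / 15% | 0 / 1.0 | +0.081 | +0.035 | within 0.004 |
| 10% / 20% | 0.5 / 1.0 | +0.075 | +0.031 | within 0.004 |
| 15% / 30% | 0.5 / 1.0 | +0.109 | +0.044 | within 0.004 |

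Rounded outward, this is +0.03 to +0.11 unadjusted and +0.01 to +0.05 adjusted. Against the planned effect, the unadjusted bias is 0.038/0.31 = 12% to 0.109/0.31 = 35%. The adjusted bias is 0.015/0.31 = 5% to 0.044/0.31 = 14%. Type I error was 7% to 14% unadjusted and 5.7% to 6.6% adjusted.

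**Step 5. Same rates and slopes, but drop-out driven by the unseen post-intervention value.**

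| Loss C / T2 | Slope C / T2 | Baseline-adjusted | Baseline and midpoint | Share remaining |
|---|---|---|---|---|
| 15% / 15% | 0.5 / 1.0 | +0.037 | +0.033 | 0.033/0.037 = 89% |
| 15% / 15% | 0 / 1.0 | +0.082 | +0.072 | 0.072/0.082 = 88% |
| 10% / 20% | 0.5 / 1.0 | +0.083 | +0.073 | 0.073/0.083 = 88% |
| 15% / 30% | 0.5 / 1.0 | +0.115 | +0.107 | 0.107/0.115 = 93% |

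**Step 6. Neutral cases.** With 15% loss in both arms and the same dependence on MVPA in both, every estimator had bias within about 0.003 SD. When drop-out was driven by baseline MVPA, baseline adjustment alone brought the bias to within 0.004 SD, and midpoint data added nothing.

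**Step 7. Cross-check.** A separate simulation used a true effect of 0.31, correlations 0.5 and 0.7, slope 1 and loss up to 30% versus 10%. With drop-out following midpoint MVPA and differing by arm, bias was +0.05 to +0.18 unadjusted, +0.02 to +0.07 baseline-adjusted, and within 0.005 with pre-drop-out data. With drop-out following the unseen outcome, pre-drop-out data removed only about 8% to 14% of the baseline-adjusted bias.

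**The case against.** The strongest defence is that the plan is open about the deviation from full intention-to-treat, promises sensitivity analyses on missing data, and may specify them in a statistical analysis plan that is not shown. That stands as far as the missing detail goes. It does not change which estimate section 10.1 makes the headline.

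Four stronger readings are tempting, and the documents do not support them.

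- A reader might infer that the comparison is valid only if missingness is unrelated to MVPA. Step 6 shows otherwise: dependence that is the same in both arms, or is captured by a covariate in the regression, leaves about no bias.
- A reader might infer that the recorded Fitbit data would remove much of the bias whatever its cause. They do so only when drop-out depends on MVPA already recorded. Women lost before the midpoint, or who never sync, contribute little or nothing.
- A reader might take 12% to 35% of the planned effect as the size of the problem. That holds only without baseline adjustment. Section 10.1 does not fix the covariates, and baseline MVPA could be one of them; the corresponding range is then 5% to 14%.
- A reader might take section 6.1 to mean that a woman who stops the modules is cut off from data collection. The section speaks of leaving the trial and does not say that skipping modules counts. Collecting nothing after a full withdrawal is ordinary. The wording is unclear, not wrong.

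Differential loss is also an assumption. The protocol gives a single attrition rate, and the incentives in section 5.1.2 apply to all arms.

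**Conclusion.** The point holds as a recommendation to improve a stated method. Section 10.1 chooses an available-case regression as primary although planned measurements of the same outcome exist for many of the women it excludes. In the scenarios examined, using those measurements removed the bias when drop-out followed midpoint MVPA, helped a little when it followed the unseen outcome, and did no material harm elsewhere.

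The size is modest and conditional: up to about 0.11 SD unadjusted and 0.05 SD baseline-adjusted at correlation 0.6, and about zero if drop-out works the same way in both arms. The correlations, slopes and arm-specific rates behind these figures are assumptions. Only the 15% overall rate, the arm sizes and the 0.31 come from the protocol. No change of sample size follows.

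**What to change.** In section 10.1, make the primary analysis a likelihood-based repeated-measures model (or multiple imputation) on all observed Fitbit MVPA from the randomised participants. Include arm by time, baseline MVPA and the stratification factors, and read the contrast at the primary time point. The protocol does not say whether baseline Fitbit MVPA is recorded before randomisation; that should be stated before it is used as a covariate. Keep the available-case regression as a sensitivity analysis, and add one that lets missing outcomes differ from what the observed data predict (missing not at random).

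In section 6.1, state that stopping module use is not drop-out, and that Fitbit data continue to be collected unless the participant withdraws consent for data. This matters most where modelling cannot help, because values recorded before drop-out do not replace outcomes never collected.

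The cost is modest extra analysis work and a sentence in section 6.1 and in the consent text. The new primary analysis relies on missing at random, a weaker assumption than the present one but still untestable.
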